1.0 Objectives

22.1 Study Objectives

Describe the purpose, specific aims or objectives. State the hypotheses to be tested.

The purpose of this study is to test the efficacy of virtual reality videos to facilitate exposure therapy in social anxiety disorder (SAD). The exposure therapy videos are the focus of this experiment. Essentially, we are testing the efficacy of the Virtual Reality Exposure Therapy (VRET) scripts (i.e., virtual scenarios, people, and interactions that we expose socially anxious people to). To this end, the goal of the current study is to help people with social anxiety overcome their phobias. Individuals who experience a difficult time building social relationships, accomplishing everyday tasks, or pursuing interviews can practice those same behaviors in a controlled environment.

The study hypotheses are as follows:

1. Virtual reality exposure therapy intervention (vs. waitlist control condition) is effective for treating SAD symptoms.
2. Participants who received the virtual reality exposure therapy will experience maintenance of treatment gains following 3-month and 6-month post-termination of treatment.
3. Users of the virtual reality exposure therapy will demonstrate high amounts of acceptability of the treatment.

22.2 Primary Study Endpoints

State the primary endpoints to be measured in the study. Clinical trials typically have a primary objective or endpoint. Additional objectives and endpoints are secondary. The endpoints (or outcomes), determined for each study subject, are the quantitative measurements required by the objectives. Measuring the selected endpoints is the goal of a trial (examples: response rate and survival).

To answer these questions, the proposed study will use both qualitative and quantitative methods. Qualitative methods will include a semi-structured interview at the end of the study to gather information on the participant's experience, as well as data collected throughout the therapy process. Quantitatively, the study proposes to use basic descriptive statistics to examine treatment outcomes and engagement with digital tools.

This exploratory study will answer the following questions:

- 1) Compared to the waitlist control condition, is the virtual reality exposure intervention more effective for treating symptoms of social anxiety disorder?
- 2) Are there higher treatment gains maintained over time among participants who receive the virtual reality exposure therapy compared to the waitlist control condition?

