After self-report questionnaires are completed, participants will then complete the baseline clinical interview (paper version of “LIMBIX - Measure - MINI Neuropsychiatric Interview.pdf”) conducted by a study team member who is not the ultimate research therapist. The clinical interview will generally take about 15 to 25 minutes. This interview will be videotaped to conduct reliability assessment on the diagnoses.

Participants who meet the study eligibility criteria will next be contacted by phone by another study team member within a week to receive their random assignment to either the virtual reality exposure therapy condition or the waitlist control condition and to schedule their treatment planning session. Participants in the immediate treatment group will be invited to start treatment soon after the baseline assessments, whereas those in the waitlist control condition will be invited to start this treatment 8 weeks later. The script “LIMBIX - Scripts - Study Therapist to Subject” will be used to facilitate this process.

Within a day the intake assessor completes the initial assessment for an eligible participant, the coordinator will (1) randomly assign the eligible participant who had just completed the interview to their treatment condition, (2) call the participant to inform them of their study condition, and (3) inform their research therapist assigned to be in charge with conducting the 8 to 10 50-minute weekly treatment planning and therapy sessions.

As participants assigned to the treatment condition will begin therapy immediately, the coordinator will communicate this message to the research therapist within a day of the initial assessment.

On the other hand, participants assigned to the waitlist control condition will begin therapy 8 weeks later, and the coordinator will communicate this message within a few weeks after the initial assessment visit.

Once the research therapist receives the message from the coordinator to start scheduling treatment with a particular participant, he or she is expected to contact the participant and set up an appointment within the next one or two weeks depending on their availability.

Step 3: Treatment Planning

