During the session, some research personnel will assist with helping participants to respond if the participants have problems responding to the system (“LIMBIX - Scripts - RA Prompts If Participant Gets Stuck.docx”).

Step 5: Between-Session Symptom Assessment

To monitor treatment progress, participants will complete between-session symptom assessments at the end of each session (“LIMBIX - Measure - Between session symptom assessments.pdf”). Participants will also be asked to engage in practice of skills they learn in treatment between sessions (refer to “LIMBIX – Between-Session Homework”).

This applies to participants in the treatment, but not waitlist, condition. For participants placed on the waitlist, this applies only once treatment has started.

Step 6: Termination

The research therapist will work with participants to determine therapy goals at the start of treatment, and will work with them to monitor progress on these goals throughout treatment. Generally, treatment length will span 8 to 10 sessions, depending on the participant’s symptoms, response to treatment, and therapists’ clinical judgment.

Step 7: Final Assessments

Participants will be asked to complete the follow-up questionnaire packet (see “LIMBIX - Measure - Follow-up questionnaire packet.pdf”). This packet will be provided to them prior to their final session, and the final interview (conducted online “LIMBIX - Measure - Final interview.pdf”) will be included in the termination session. The final interview session will be administered at the end of Session 10.

Three and six months after treatment, participants will be contacted online to complete the 3-month and 6-month follow-up questionnaires (see “LIMBIX - Measure - 3-month post-treatment.pdf” and “LIMBIX - Measure - 6-month post-treatment.pdf” accordingly). At this time, participants will only complete self-report measures online.

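### Hypothesis 2 states maintenance of gains with no comparator, but primary question 2 asks for higher maintained gains than a waitlist that is itself offered the treatment, so a lasting effect is expected to give a null answer to question 2

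*Combined protocol and SAP*

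**What the plan says.** Maintenance of gains is stated in two ways.

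- Section 22.1 (Study Objectives), hypothesis 2: "Participants who received the virtual reality exposure therapy will experience maintenance of treatment gains following 3-month and 6-month post-termination of treatment". It names no comparator, although hypothesis 1 in the same list explicitly sets VRET against the waitlist.
- Section 22.2 (Primary Study Endpoints), question 2: "Are there higher treatment gains maintained over time among participants who receive the virtual reality exposure therapy compared to the waitlist control condition". Here the comparator is the waitlist. Section 7.1 likewise puts the waitlist comparison and the two follow-ups in one sentence.

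Section 7.2 settles what the waitlist arm receives and when follow-up occurs. In Step 2, "those in the waitlist control condition will be invited to start this treatment 8 weeks later". In Step 7, "Three and six months after treatment, participants will be contacted online to complete the 3-month and 6-month follow-up questionnaires", with no separate rule for the waitlist arm.

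Section 8.3 plans growth curve models with individual trajectories and a test of time from post-treatment through follow-up. It names no group term and does not say which statement of maintenance decides.

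**The concern.** The two statements need different comparisons. Hypothesis 2 reads naturally as a within-participant claim: people who had the treatment keep what they gained. Question 2 is a between-arm claim. They would agree if the control arm stayed untreated through follow-up, but here it is offered the same treatment and then followed from the end of that treatment.

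One of the two primary questions is therefore posed so that an effective, durable treatment is expected to show no difference. A report that follows section 22.2 as worded could conclude that higher maintained gains were not shown while the same data support hypothesis 2. A positive between-arm result would be no easier to read, because it could come from waitlist participants who never took up treatment.

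**Working it through.** **The plan's own figure.** Section 8.2 gives 300 per intervention group at 80% power and two-sided alpha 0.05, but no numerical effect size, so the figure cannot be reproduced forwards. Back-solving for 300 versus 300 gives d = (1.96 + 0.842) × √(2/300) = 0.229. The point does not rest on this figure.

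**Timeline.** Inputs from section 7.2:
- the 8-week wait;
- the scheduling step ("set up an appointment within the next one or two weeks depending on their availability"), taken as 0 to 2 weeks;
- weekly sessions, where "treatment length will span 8 to 10 sessions".

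Three months is counted as 13 weeks and six months as 26. Weeks run from baseline.

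| | Immediate VRET | Waitlist participant who accepts |
|---|---|---|
| Start | 0–2 | 8–10 |
| End of treatment | 8–12 | 16–20 |
| 3 months after own treatment | 21–25 | 29–33 |
| 6 months after own treatment | 34–38 | 42–46 |

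The latest waitlist finish (week 20) precedes the earliest 3-month visit in the immediate arm (week 21). On this schedule the waitlist has completed VRET before that visit, whether follow-up is dated from each person's own termination or from randomisation.

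**Expected between-arm difference.** Let d be the gain retained at follow-up relative to no treatment, in SD units and equal for immediate and delayed starters. Let q be the share of the waitlist that never takes treatment. Then

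difference = d − [(1 − q) × d + q × 0] = q × d.

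With full uptake (q = 0) this is zero for every d, including d = 0. The contrast then cannot tell a lasting benefit from one that has vanished.

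**Chance that the between-arm test favours VRET.** Section 8.2 gives 600 in the two VRET conditions combined and 150 on the waitlist. With SD 1, SE = √(1/600 + 1/150) = 0.0913. For a two-sided 5% test, P = Φ(q × d / 0.0913 − 1.96).

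| Untreated share q | d = 0.3 | d = 0.5 | d = 0.8 | d = 1.0 |
|---|---|---|---|---|
| 0 | 2.5% | 2.5% | 2.5% | 2.5% |
| 0.1 | 5.1% | 7.9% | 13.9% | 19.4% |
| 0.2 | 9.6% | 19.4% | 41.8% | 59.1% |
| 0.5 | 37.6% | 78.2% | 99.2% | >99.9% |

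For example, q = 0.2 and d = 0.8 give 0.16 / 0.0913 = 1.753, and Φ(1.753 − 1.96) = 0.418.

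**Within-participant test in the same scenario.** Take the change from post-treatment to 6 months in the 600 immediate starters, true change zero, with an assumed margin of 0.2 SD. For within-person correlation ρ, SE = √(2(1 − ρ)) / √600. The probability of success is Φ(0.2/SE − 1.96): 98.5% at ρ = 0.3, 99.8% at ρ = 0.5 and about 100% at ρ = 0.7.

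**Simulation** (4,000 runs, d = 0.8 at end of treatment, ρ = 0.5, full uptake). If the gain lasts, the within-participant test succeeds in 99.9% of runs and the between-arm contrast on change from baseline favours VRET in 2.5%. If the gain is fully lost, the figures are 0% and about 3%.

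**Why change from baseline should not decide.** Suppose a gain of 0.8 SD falls to 0.3 SD. With SD of change 1, the test against baseline gives z = 0.3 × √600 = 7.3, or 0.3 × √750 = 8.2. It would declare success although most of the gain has gone.

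**The case against.** - **The analysis section already leans one way.** Section 8.3 models individual trajectories over time and names no group contrast, which fits hypothesis 2. This stands in part: the plan is not silent. But the section does not say that it overrides the waitlist comparison in section 22.2.
- **The study is exploratory and descriptive.** Section 22.2 says so. Question 2 is nevertheless listed as primary, section 8.3 plans inferential models, and a descriptive difference near zero would mislead in the same way.
- **The 2.5% is circular.** It is one tail of the 5% test, which follows once equal benefit and full uptake are assumed. This stands. It illustrates what question 2 asks for and is not a forecast for this trial. The waitlist is only invited to start, so uptake may be incomplete; hence the range in the working.
- **The comparator may be the untreated wait.** With an end-of-wait score, retained gains could be set against untreated change, so a reader should not infer that question 2 could never be answered. However, no such assessment is described. Of the between-session measures, Step 5 says "For participants placed on the waitlist, this applies only once treatment has started". An untreated score at about weeks 8 to 10 would also not be a concurrent control for follow-up months later.
- **A reader might infer that VRET would look worse than waitlist.** The documents do not support that. The two statements diverge as supported versus null. The simulation gives a reversed effect only if an end-of-wait score served as the waitlist's post-treatment anchor, and the plan has no such score.

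**Conclusion.** The mismatch is real and should be corrected. Sections 22.1 and 22.2 state the maintenance objective with different contrasts, and nothing in the plan says which governs. If VRET works, lasts and is taken up by most of the waitlist, hypothesis 2 is supported and question 2 returns a null.

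The chance of a between-arm result favouring VRET is about 2.5% under full uptake. With an assumed 20% of the waitlist untreated, it is about 10% at d = 0.3 and 59% at d = 1.0. Any such difference arises only through non-uptake, so it cannot be read as evidence on durability. With many decliners the contrast regains power and the conflict weakens.

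The effect sizes, correlation, margin, uptake shares and equal response in immediate and delayed starters are assumptions; the documents give none of them. Reading hypothesis 2 as within-participant is an inference from its wording, since it specifies no test.

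**What to change.** 1. In section 22.2, reword primary question 2 to match hypothesis 2: among participants who receive VRET, are gains kept at 3 and 6 months after termination? Delete the closing comparison with the waitlist.
2. In sections 22.2 and 8.3, name the deciding contrast for maintenance: the within-participant change from post-treatment to 3 and 6 months, timed from each person's own termination, in immediate and delayed starters. Report change from baseline as supportive only.
3. State that this result is uncontrolled, and that between-arm differences at follow-up will not be read as evidence on durability.

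The cost is a few sentences, with no new visits or data, because Step 7 already plans the end-of-treatment and follow-up questionnaires. The price is that durability is openly reported as an uncontrolled within-group result.

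Three matters are separate. The randomised VRET–waitlist contrast belongs to the period before the waitlist is treated, but it needs an end-of-wait assessment that the protocol does not describe, so it is not part of this no-new-data fix. How much loss still counts as maintenance is also unstated. Section 8.3 lists follow-up at 6 and 12 months, and its new wording should use the 3 and 6 months given in sections 22.1, 7.1 and 7.2.

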3.3 Early Withdrawal of Participants

3.3.1 Criteria for removal from study

Insert subject withdrawal criteria (e.g., safety reasons, failure of subject to adhere to protocol requirements, subject consent withdrawal, disease progression, etc.).

1. If a participant no-shows to 4 sessions in a row or 6+ sessions in a 2-month period.
2. If a participant’s symptoms increase to the point that more intensive care than can be provided through this study is required.

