In each session, the participant will come in and be exposed to different social scenarios virtually. Each study team member follows a script for each session to direct them to the scenario (“LIMBIX - Scripts - Each Session - V1.docx”). The team member thus functions mainly as a facilitator who will ensure that the correct brief social scenario is presented to the participant for both the general social skills exposure therapy (“LIMBIX - Scripts - Phobia General Social Interactions.docx”) and job interview exposure therapy (“LIMBIX - Scripts - Phobia Job Interview.docx”). Note that there are seven social scenarios for both forms of exposure therapy. The social scenarios build on each other in terms of the level of difficulty. Therefore, we will continue with the next scenario only after the participant says he or she feels ready to expose themselves to the next scenario. After each scenario, the study team member records participants' subjective units of distress using the “LIMBIX - In-session SUDS Ratings”. Ten minutes before the 50-minute session ends, the team member assigns homework in between the

weekly sessions using a standard script (“LIMBIX – Between Session Homework”). Homework is meant to help participants generalize the skills they learn from this treatment to their everyday life situations.

Step 4: Assessing and Adjusting Treatment

We aim to ensure that each participant finds the intervention to be helpful and to identify the need to discontinue due to various reasons (e.g., participant finds the intervention is unhelpful, causes adverse side effects or severe cybersickness). Participants will thus complete the System Usability Scale on the first, fourth, and last week of the 8-10 session intervention. This will provide a measure of their experience and will help to facilitate a conversation with the therapist about their experience. Scores below a 70 (Bangor, Kortum, & Miller, 2009) would indicate that the usability of the tool was below average and will signify that further discussion is needed to identify if the use of the digital tool should be discontinued. Please note that efforts will be made to problem solve usability concerns with the participant when possible, as participants will have varying levels of technological comfort the therapist will work to personalize this process to the participants’ needs.

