22.4.3 Method for Assigning Subject to Treatment Groups

Describe the randomization process and how the associated treatment assignment will be made.

Using a random number generator with the “RAND” function on Microsoft Excel, the participants will be randomly allocated to either one of the two treatment conditions (General Social Skills training or Job Interview training) or waitlist condition.

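### Primary question 2 defines the VRET side by receipt and the control side by condition, and no as-randomised analysis set corrects it

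*Combined protocol and SAP*

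**What the plan says.** Section 22.2 lists two primary questions. The first is framed by intervention and condition: "Compared to the waitlist control condition, is the virtual reality exposure intervention more effective for treating symptoms of social anxiety disorder". The second asks about gains kept over time "among participants who receive the virtual reality exposure therapy compared to the waitlist control condition". Hypothesis 2 in Section 22.1 also uses receipt, but describes one group with no comparator: "Participants who received the virtual reality exposure therapy will experience maintenance of treatment gains".

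Allocation is random. Section 22.4.3 says "the participants will be randomly allocated to either one of the two treatment conditions (General Social Skills training or Job Interview training) or waitlist condition". Section 8.2 plans 300 participants in each of the two VRET conditions and 150 on the waitlist. Under Section 7.2 (Step 2), people learn their arm by phone after the eligibility interview, the therapist then arranges an appointment, and "those in the waitlist control condition will be invited to start this treatment 8 weeks later".

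Section 3.3.1 removes people on two grounds: "If a participant no-shows to 4 sessions in a row or 6+ sessions in a 2-month period" and "If a participant’s symptoms increase to the point that more intensive care than can be provided through this study is required". Section 3.3.2 keeps data gathered before withdrawal and asks for no post-treatment or follow-up assessment afterwards.

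Section 8.3 names growth curve models and software. It gives no analysis population, no rule that participants are analysed as assigned, and no missing-data rule.

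**The concern.** A randomised comparison is fair because chance alone decides who is on each side. Question 2 replaces that on the VRET side with receipt, which depends on what people do once they know their arm. The waitlist side remains everyone given that condition. An analyst could follow the wording in good faith, exclude VRET-assigned people who never attended, and keep their counterparts on the waitlist, who have no sessions to miss while they wait.

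If people who never start differ in prognosis from those who do, the two sides differ even when the treatment does nothing. The wording also fails to separate the groups: a waitlist member treated after week 8 is both someone who receives VRET and a member of the waitlist condition.

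**Working it through.** **1. Who is compared.** Question 1 sets intervention against condition. Question 2 sets receivers against condition. Sections 7.2 and 22.4.3 describe groups by random assignment but do not say who is analysed, and Section 8.3 does not either. Nothing overrides the wording of question 2.

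**2. Who leaves the VRET side.** Someone told by phone that they are in VRET who never attends has not received it. These never-starters are the clear exclusions. *Receive* is given no minimum, so a person who attended some sessions is not clearly excluded.

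**3. Who fits both groups.** The VRET arm has 8 to 10 weekly sessions, with follow-up 3 and 6 months after they end. The waitlist is invited to start at 8 weeks. By every follow-up that question 2 concerns, the waitlist has been offered VRET.

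**4. The plan's own figure.** Section 8.2 states 300 per intervention group, two-sided 0.05 and 80% power, but no effect size, so 300 cannot be reproduced. It can only be inverted. For 300 against 300, d = (1.960 + 0.842) × √(2/300) = 0.229. For 600 pooled against 150, d = 2.802 × √(1/150 + 1/600) = 0.256. The point does not depend on these values; they give a scale.

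**5. Size of the bias before crossover.** Let q be the share of the 600 VRET-assigned who do not receive treatment, and g the SD by which receivers would do better than non-receivers regardless of treatment. Both are assumptions. If receivers have mean m, the whole arm has mean (1 − q)m + q(m − g) = m − qg. Keeping receivers only therefore shifts the contrast by q × g.

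With no true effect and an intact, untreated waitlist of 150:
- SE = √(1/(600(1 − q)) + 1/150)
- two-sided error = P(|Z + qg/SE| > 1.96)

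| q | g (SD) | bias (SD) | SE | two-sided error |
|---|---|---|---|---|
| 10% | 0 | 0 | 0.092 | 5.0% |
| 10% | 0.2 | 0.02 | 0.092 | 5.5% |
| 10% | 0.5 | 0.05 | 0.092 | 8.4% |
| 20% | 0.3 | 0.06 | 0.094 | 9.8% |
| 20% | 0.5 | 0.10 | 0.094 | 18.8% |
| 30% | 0.5 | 0.15 | 0.095 | 35.1% |
| 20% | −0.5 | −0.10 | 0.094 | 18.8%, almost all against VRET |

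Example, 30% and 0.5: SE = √(1/420 + 1/150) = 0.0951; 0.15/0.0951 = 1.577; P(Z > 1.960 − 1.577) = 35.1%, and the other tail is negligible.

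**6. Loss on both sides.** If the waitlist loses a share r with the same prognosis gap, the bias is (q − r) × g. At 20% and 20% it is 0. At 30% and 10% with g = 0.5 it is 0.10 SD.

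**The case against.** The strongest reply is that question 2 is a plainly worded research question in a study that Section 22.2 calls exploratory, and not a definition of an analysis set. Question 1 and hypothesis 1 carry no receipt wording, and Section 8.3 nowhere restricts the models to receivers. This stands to the extent that the documents state no plan to drop non-receivers. It does not remove the problem: question 2 is listed as primary, no other text says who is compared, and the two primary questions can be read as using different populations.

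A reader might infer that everyone who stops early also leaves the VRET side. The documents do not support that. With no minimum for receipt, a person who attended some sessions has arguably received VRET. The usability check, after which "further discussion is needed to identify if the use of the digital tool should be discontinued", concerns people already using the tool, and data up to withdrawal are kept. Their later outcomes are lost through Section 3.3.2, which applies to both arms and is a separate matter.

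A reader might also infer that the contrast is bound to favour VRET. That is plausible during the wait, because only people with sessions can be removed for missing them. Against it, the worsening rule is not limited to one arm, treated waitlist members later come under the same no-show rule, and offering them VRET may pull the follow-up contrast towards no difference. No dropout rate or prognosis is given.

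Finally, the error rates rest on assumed q and g, and the 35% needs both at the top of their range. That is accepted.

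**Conclusion.** The point holds as a gap in definition. Question 2 is worded by receipt on one side and by condition on the other, and nothing in Section 8.3 restores comparison by randomised arm. Read as written, never-starters are left out of one arm only and treated waitlist members fit both groups.

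For 10% to 30% non-receipt and a gap of 0 to 0.5 SD, the bias is 0 to 0.15 SD and the two-sided error 5% to 35%. The top of that range is 0.15/0.256, or about 59%, of the effect that 600 against 150 could detect with 80% power. These figures apply only against an untreated waitlist, so they do not predict the 3- and 6-month results. The sign is not established: the bias is zero if never-starters have the same prognosis as receivers, and it reverses if theirs is better. The change should be made, but the documents do not show that the trial's result will be biased towards VRET.

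**What to change.** 1. In Section 22.2, word both primary questions as participants randomised to VRET against participants randomised to waitlist.
2. In Section 8.3, state that every randomised participant is analysed in the assigned arm whatever the attendance, including those who never start. Include the baseline score, which is already collected but is not among the time points listed there, so that never-starters contribute to the growth model.
3. Send the existing online questionnaires to never-starters and to people who stop sessions but have not withdrawn consent. Rewording alone is not enough, because Section 7.2 (Step 7) ties the final questionnaires to the last session, and never-starters have none. Reconcile this with Sections 3.3.1 and 3.3.2 by stating whether removal from treatment also ends data collection.
4. Limit the controlled contrast to the period before the waitlist starts VRET. This needs an outcome in both arms at a common time before then. Section 7.2 schedules none for the untreated waitlist.
5. Label any result in those who received VRET (hypothesis 2) as a non-randomised, within-person description.

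The cost is a somewhat smaller estimated effect and some extra online questionnaires. If 20% never start and gain nothing, 0.50 SD in receivers becomes 0.80 × 0.50 = 0.40 SD by assignment before crossover. Over the assumed range, never-starters number 60 to 180 of 600, and the end-of-wait assessment adds up to 150 waitlist members. The change alters no treatment.
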